7.5 Patient Compliance Document

Study staff will provide the patients with the **S1600** Patient Intake Calendar ([Section 18.4](#)) for his/her completion. (NOTE: There are two calendars: one for Before Surgery and one for After Surgery.) The patient will complete this intake calendar, recording daily consumption in servings (complete, half or no intake) during pre-op and post-op and return the Before Surgery calendar on the day of surgery and the After-Surgery calendar at the 30-day follow-up visit. Study staff will review and ascertain patient adherence at the end of preoperative treatment and postoperative treatment. The study staff will report drink adherence on the **S1600** Treatment Form (Preoperative and Postoperative). The **S1600 Patient Intake Calendar** will be used as a source of evaluation of patient compliance and is expected to serve as a self-reminder and motivational tool for patients to comply with the recommended intake of nutritional support for this study. (NOTE: Compliance will be based on day counts of the study products consumed and confirmed at the end of the study with retrospective plasma fatty acid analysis. See [Section 18.2](#)) The completed patient intake calendar should be kept in the patient's clinic chart. Note that the calendar is provided only as a tool for tracking patient compliance. Do not submit patient calendars to the SWOG Data Operations Office.

7.6 Follow-up Visit (Day 2 after Surgery)

- a. Patients will have a blood draw for laboratory tests and sample submission for translational studies (see [Section 15.1](#)). This will take place on Day 2 after surgery, regardless of what day diet is resumed.
 - Laboratory tests: complete blood count (CBC) with differential, and (if clinically indicated) albumin and prealbumin
 - Blood draw for submission (see [Section 15.1](#)). NOTE: The blood for submission and for laboratory tests must be from the same blood draw.

The patient will be administered the **S1600** Wong-Baker FACES® Pain Rating Scale (FACES). See [Section 15.3](#) for instructions for administration of patient questionnaires.

7.7 Follow-up Visit (Day 30 after Surgery, ± 7 days)

- a. Call the patient prior to 30-day follow-up to remind them to bring their stool samples to the visit. If patient does not bring the samples, the site will send a mailer home with instructions to the patient to ship their stool samples to the SWOG Biospecimen Bank (ambient). Sites will be instructed to add a comment in the SWOG Specimen Tracking System.
- b. The patient will be assessed by the surgeon for surgical complications per Clavien-Dindo grading (see [Section 10.1a](#)) on the **S1600** 30-Day Post-Op Assessment Form and the form must be signed by the surgeon.
- c. Patients will have a DXA Scan and a blood draw for laboratory tests and sample submission for translational studies (see [Section 15.1](#) and [Section 18.3](#)).
 - Laboratory tests: complete blood count (CBC) with differential, and (if clinically indicated) albumin and prealbumin.
 - Blood draw for submission (see [Section 15.1](#)). NOTE: The blood for submission and for laboratory tests must be from the same blood draw.
- d. Patients will complete the following questionnaires:
 - **S1600** Functional Assessment of Anorexia Cachexia (FAACT) Questionnaire
 - Scored Patient-Generated Subjective Global Assessment (PG- SGA). NOTE: Clinician will also complete a portion of this form. Refer to [Section 7.1a](#) for patient and clinician instructions.
 - **S1600** Wong-Baker FACES® Pain Rating Scale (FACES).
- e. The study staff must complete the **S1600** Cover Sheet for Patient-Completed Questionnaires as well as complete and submit required forms per [Section 14.4](#).
- f. Patients will be called by staff at the EDGE Research Laboratory for completion of two 15-minute 24-hour dietary recall phone interviews (for one weekday and one weekend day) (see [Section 15.4](#)).
- g. The study staff should collect the completed **S1600** Patient Intake Calendar – After Surgery from the patient.

7.8 Follow-up Visit (90 Days after Surgery, ± 7 days)

The patient will be assessed by the surgeon for late-phase surgical complications per Clavien-Dindo grading (see [Section 10.1a](#)) on the 90-Day Post-Op Assessment Form and the form must be signed by the surgeon.

7.9 Criteria for Removal from Protocol Treatment

- a. Patient has completed protocol treatment and the **S1600** 90-day Post-Op Assessment Form has been submitted.
- b. Patient does not consume ≥ 80% (12 of 15 bottles) of pre-surgical supplementation.
- c. Patient does not undergo planned radical cystectomy surgery.
- d. Patient requires tube feeding any time prior to completion of 10 days of study drink.
- e. Patients may withdraw from the protocol treatment at any time for any reason.

7.10 Discontinuation of Treatment

All reasons for discontinuation of treatment must be documented on the **S1600** Off Protocol Notice.

NOTE: Patient follow-up must be completed and forms must be submitted for all patients regardless if the Off Protocol Notice is submitted prior to completion of [Section 7.9a](#).

7.11 Follow-Up Period

All patients will be followed for 3 years after radical cystectomy surgery or until death, whichever occurs first. See [Section 9.0](#) and [Section 14.4i](#) for follow-up and forms submission guidelines. See COVID-19 Guidance in [Section 7.13](#).

7.12 Unblinding

Patients may be unblinded to their treatment assignment on request at the end of the study, after study results have been published. Institutions will be notified when patient unblinding information is available for the study. For emergency unblinding criteria and procedures, see [Section 18.8](#).

7.13 COVID-19 Guidance

Patient-Reported Outcome Questionnaires via Telemedicine (Phone or Virtual Visit), please see [Section 15.3](#).

Follow-up Visits via Telemedicine (Phone or Virtual Visit):

- Follow-up visits at timepoints indicated in [Section 9.0](#), Footnote (H) of the Study Calendar may be conducted via telemedicine (Phone or Virtual Visit) to provide continuity of care and patient follow-up provided that the Responsible Investigator determines that the phone/virtual visit is adequate to achieve the central purpose of the visit and assure the safety of the patient.
- Study visits may also be delayed or missed if in the judgment of the Responsible Investigator the benefit of delay/omission of a visit outweighs the risks of exposure

of the patient to the virus by coming in for an in-person visit and an alternative method (phone or virtual visit) is not possible.

- The above alterations would need to be thoroughly documented in the medical record by the Responsible Investigator with the reason for the deviation and brief justification for why the deviation was considered to be minor (e.g., routine follow-up on patient no longer on active therapy).

8.0 TOXICITIES TO BE MONITORED AND DOSE MODIFICATIONS

8.1 NCI Common Terminology Criteria for Adverse Events

This study will utilize the CTCAE (NCI Common Terminology Criteria for Adverse Events) Version 5.0 for toxicity and Serious Adverse Event reporting. A copy of the CTCAE Version 5.0 can be downloaded from the CTEP home page (<http://ctep.cancer.gov>). All appropriate treatment areas should have access to a copy of the CTCAE Version 5.0.

8.2 Dose Modifications

- Before surgery, no dose modifications will be allowed.
- Mild gastrointestinal upset, loose stools and nausea after supplementation may occur. After surgery, if the patient feels bloated, nauseated, or is burping excessively, then he or she will be allowed to wait to resume a few hours before trying the drinks again. If resumption of diet is delayed (within 72 hours of surgery), patients will resume the supplement once they can tolerate it and resumption is cleared by the treating physician.

8.4 Adverse Event Reporting

Toxicities (including suspected reactions) that meet the expedited reporting criteria as outlined in [Section 16.1](#) of the protocol must be reported to the Operations Office, Study Chair and NCI via CTEP-AERS, and to the IRB per local IRB requirements.

9.0 STUDY CALENDAR

REQUIRED STUDIES	Pre-Study	Baseline ^A	D -5	D -4	D -3	D -2	D -1	Day 0 SURGERY ^K	D 1	D 2	D 3	D 4	D 5	D 30 ^J	D 90 ^J	F/U ^H
PHYSICAL																
Medical History & Comorbidities	X	X												X	X	
Zubrod Performance Status		X								X				X		
Body Weight & Height	X	X												X		
Assess Surgical Complications ^B														X	X	
Recurrence Assessment														X	X	X
Review Intake Calendar ^C									X					X		
SPECIMENS																
Blood per Section 15.1		X								X				X		
Stool per Section 15.2 (Optional)		X		X						X						
LABORATORY																
Prealbumin, if clinically indicated		X								X				X		
Albumin, if clinically indicated		X								X				X		
CBC with Differential, Platelets		X								X				X		
SCANS																
DXA Body Composition		X												X		
SURGERY																
Radical Cystectomy								X								
PATIENT COMPLETED QUESTIONNAIRES																
S1600 FAACT ^E		X												X		
S1600 PG-SGA ^G	X													X		
S1600 Pain Scale FACES ^E		X								X				X		
S1600 Patient Intake Calendar			X	X	X	X	X		X	X	X	X	X			
Phone Interview ^F		X												X		
Blinded Nutritional Drink			X	X	X	X	X		X	X	X	X	X			

Click here for [Footnotes](#)

NOTE: Forms are found on the protocol abstract page of the CTSU website (www.ctsu.org). Form submission guidelines are found in [Section 14.0](#).

NOTE: Unless indicated otherwise in the protocol, scheduled procedures and assessments (treatment administration, toxicity assessment for continuous treatment, disease assessment, specimen collection and follow-up activities) must follow the established SWOG guidelines as outlined in <https://www.swog.org/clinical-trials/protocol-workbench>.

Footnotes:

- ^A Baseline is after registration and before beginning preoperative nutrition drinks.
- ^B Includes Clavien-Dindo (I-V) grading (see [Table 1](#) in Section 10.1a)
- ^C Site personnel to review patient reported compliance for preoperative period at the time of surgery, and post-operative period on Day 30 ± 7 days (see [Section 7.5](#)).
- ^E See [Section 15.3](#) for further details.
- ^F The site must complete the **S1600** Telephone Contact Form and FAX it to the EDGE Laboratory at [name] within 24 hours after registration. Please phone the EDGE lab at [name] to ensure the FAX was received. Nutrition staff from the EDGE Research Laboratory will contact patients directly by phone to conduct diet recall interviews (see [Section 15.4](#)).
- ^G The Scored Patient-Generated Subjective Global Assessment (PG-SGA) will be completed by the patient and the clinician (see [Section 7.1a](#)).
- ^H Includes recurrence and vital status at Months 3, 6, 9, 12, 18, 24 and 36 months after radical cystectomy surgery or until death. See [Section 14.4j](#). See COVID-19 Guidance in [Section 7.13](#).
- ^J Day 30 visit to take place within 7 days before or after Day 30 (after surgery date). Day 90 visit to take place within 7 days before or after Day 90 (after surgery date).
- ^K **Because blood samples are required to be collected and shipped on Day 2 following surgery (see Section 15.1), surgery should take place on a Monday, Tuesday, or Wednesday.**

10.0 CRITERIA FOR EVALUATION AND ENDPOINT ANALYSIS

10.1 Measurement of Complications

a. **Primary Endpoint: Post-operative Complications** A post-operative complication is defined as a binary indicator variable indicating whether the patient experienced any complication (any/none; Clavien-Dindo grades I-V; Table 1). (118)

Table 1. Clavien-Dindo Scheme

Clavien-Dindo Grades	Definition
Grade I	Any deviation from the normal postoperative course without the need for pharmacological treatment or surgical, endoscopic or radiological interventions. Allowed therapeutic regimens are drugs as antiemetic, antipyretics, analgesics diuretics, electrolytes, and physiotherapy.
Grade II	Requiring pharmacological treatment with drugs other than such allowed for grade I complications. Blood transfusions and total parenteral nutrition are also included.
Grade III	Requiring surgical, endoscopic or radiological intervention
Grade IIIa	Intervention not under general anesthesia
Grade IIIb	Intervention under general anesthesia
Grade IV	Life-threatening complications (including central nervous system complications) requiring intermediate care or intensive care unit management
Grade IVa	Single-organ dysfunction (including dialysis)
Grade IVb	Multi-organ dysfunction
Grade V	Death of a patient
Suffix “d”	If the patient suffers from a complication at the time of discharge, the suffix “d” (for “disability”) is added to the respective grade of complication. This label indicated the need for a follow up to fully evaluate the complication.

10.2 Secondary Endpoints

a. In addition to grading, complications will be defined using surgery-specific categories (ileus, deep vein thrombosis, pneumonia, wound infection, urinary tract infection, return to operation room, pulmonary embolus, myocardial infarction, cerebral vascular accident, dehiscence, sepsis, respiratory failure, bowel leak, urine leak, small bowel obstruction, death, or other). Post-operative ileus will be defined as a delay in feeding of greater than or equal to five days post-operatively.

b. **Postoperative Infections.** Infectious complications are defined by the use of non-prophylactic antibiotics to treat infection. In addition, infections will be categorized by intra-abdominal infection or surgical site infection.

- c. **Anthropometrics & Body composition.** Changes in fat mass and non-bone lean tissue (muscle mass) will be assessed by dual-energy X-ray Absorptiometry (GE Lunar DXA, Software version 13.5 or newer version, Madison, WI, or Hologic, Software version APEX 5.5.3.1 or newer version) at baseline and 30 days. The fat-free mass index (FFMI) and the appendicular skeletal muscle will be examined over time. Body weight (in a hospital gown without shoes) will be measured using a digital scale accurate to ± 0.1 kg. Height will be determined using a wall-mounted stadiometer (± 0.1 cm). See [Appendix 18.3](#) for further information.
- d. **Quality of Life.** Functional Assessment of Anorexia/Cachexia Therapy (FAACT) will be completed by the patient at baseline and 30 days post-operation. (119) The FAACT trial outcome index and anorexia subscales were used in our pilot and the SIM showed better scores than the ONS group but the differences were not statistically significant ($P=0.15$ for both), but the pilot was underpowered for this outcome. Also, the anorexia and cachexia subscale asks about issues common after RC such as: taste alterations, appetite, early satiety, and pain while eating. These data are crucial for optimizing nutrition interventions to help patients.
- e. **Readmission Rates.** Readmission will be defined as admission to any hospital after discharge home until 90 days after surgery. The reason for readmission will be recorded.

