1.2 Secondary Objectives

- a. To assess whether SIM use compared to ONS reduces late-phase post-operative complications within 90 days after scheduled RC.
- b. To assess whether SIM use compared to ONS reduces infections.
- c. To assess whether SIM use compared to ONS reduces skeletal muscle wasting.
- d. To assess whether SIM use compared to ONS reduces high grade post-operative complications.
- e. To assess whether SIM use compared to ONS reduces readmission rates.
- f. To assess whether SIM use compared to ONS improves quality of life.
- g. To assess whether SIM use compared to ONS improves disease-free survival after surgery and overall survival.

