 - 4. If patient feels too bloated, nauseous, or exhibits excessive burping, or hiccuping, then it is permissible to stop and wait for several hours before trying another feeding.
 - 5. Patient can receive other food (e.g., regular diet) if allowed by the surgeon, but minimize sugary drinks or foods (sodas, juices, gelatin).
- d. The study staff are responsible for getting the remainder of patient-specific study product (15 drink bottles) to the post-op unit for the nurse or dietitian there to dispense to the patient starting the day following surgery as described in [Section 7.3a](#). If the patient is discharged from the hospital before consuming all 5-day supply of study product, the remaining should be sent home with instructions to continue until all are consumed.
- e. If patient consented to participating in specimen banking, provide the patient with the kit for stool sample collection for first bowel movement after hospital discharge per [Section 15.2](#).

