11.0 STATISTICAL CONSIDERATIONS

11.1 Primary Analysis

The primary objective is to compare, by arm, the proportion of patients who experience any complication (Clavien-Dindo grades I–V) by day 30 after surgery. Prior evidence suggests that approximately 65% of patients will experience complications by Day 30. (120, 121, 122, 123) The design stipulates that a 35% relative reduction in the complication rate due to the intervention would be clinically meaningful, representing a reduction in the complication rate from 65% down to 42% (a 23% absolute reduction). The design also anticipates a 5% non-adherence rate (which reduces the nominal effect size). Based on a two-arm binomial design with continuity correction, a one-sided alpha = 0.05 test and 80% power, a total of 146 eligible, randomized patients will be needed. In addition, in this population, it is anticipated that 20% of patients will drop out after surgery by Day 30, and a small portion of patients (3%) will drop out prior to surgery. Incorporation of this dropout rate inflates the required sample size by a factor of $146/0.77 = 190$ eligible patients. Finally, assuming a 5% ineligibility rate, a total of 200 registered patients will be required. The high-grade complication rate (Clavien Dindo scheme III–V) will also be examined. If the control arm high grade complication rate is 20%, 200 patients will give $\geq 80\%$ power to detect an absolute reduction of 15% (down to 5%).

The primary analysis will be based on a multivariable logistic regression under intent-to-treat among all randomized patients, irrespective of their eligibility status, adjusting for the specified stratification factors: a. Diversion type (neobladder vs. ileal conduit); b. Prior neoadjuvant chemotherapy (any vs. none); and c. Nutrition status (well-nourished vs. moderate malnutrition). A Fisher's exact test will also be conducted to establish whether the results are sensitive to model assumptions. A single interim analysis for efficacy will be conducted when 50% of patients achieve their endpoint at the alpha=0.005 level. Accordingly, the final analysis will be conducted at the alpha=0.045 level. A separate analysis among all eligible randomized patients will also be conducted.

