11.2 Secondary Analysis

A set of secondary objectives will also be examined. Additional factors that are potentially prognostic for complication rates will be examined as covariates in separate logistic regression analyses, to assess the sensitivity of the primary logistic regression model

results to additional covariate adjustment; factors include BMI (< 30 vs. \geq 30), age (< 65 vs. \geq 65 years), gender (male vs. female), diabetes mellitus, pathologic staging, pro-inflammatory cytokines known to affect appetite, background diet, current use of supplements, and any autoimmune disease. Also, in addition to the primary endpoint assessment of any complication at Day 30, we will assess the complication rate at day 90, as well as a composite endpoint with three levels (complications by Day 30, complication after Day 30 but by Day 90, and no complications by Day 90). In addition, we will examine the impact of SIM use on the Day 30 and Day 90 rates of infection (as determined by antibiotic use outside of prophylaxis), skeletal muscle mass, high-grade post-operative complications (Clavien Dindo Grades III–V), and readmission rates. To consider whether dropout may be non-random (i.e., informative), which could influence the results, a sensitivity analysis will be conducted that counts dropouts as events. Although death rates are anticipated to be low, 2-year overall survival by arm will be explored using Kaplan Meier curves, as will disease-free survival. The relationship between compliance and outcomes will be explored. A set of tertiary objectives will also be examined as indicated in [Appendix 18.2](#).

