18.9 Translational Medicine Study Stool Microbiome

The stool microbiome of patients in a randomized control trial of perioperative immunonutrition for reduction of complications following radical cystectomy and urinary diversion.

a. Objectives:

1. To describe the microbiome of the gut in patients undergoing radical cystectomy and urinary diversion prior to initiation of immunonutrition or a nutrition control.
2. To define the microbiome change in patients undergoing radical cystectomy and urinary diversion after they have received blinded immunonutrition or control nutritional supplement.
3. To correlate cancer treatments, postoperative complications, specifically infections, and nutritional status with microbiome composition

b. Background

Radical cystectomy is associated with significant complication rates; most studies find 60% complication rates across the world and 30% readmission rates. The **S1600** clinical trial is examining a novel immunonutritional intervention with the goal of reducing these post-operative complications.

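### Read literally, the readmission definition in Section 10.2e omits readmissions made directly from a rehabilitation or nursing facility

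*Combined protocol and SAP*

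**What the plan says.** Readmission is a named secondary objective (Section 1.2e): "To assess whether SIM use compared to ONS reduces readmission rates". Its only definition is in Section 10.2e: "admission to any hospital after discharge home until 90 days after surgery". The next sentence adds: "The reason for readmission will be recorded".

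Section 11.2 lists readmission rates among the secondary outcomes to be compared by arm. It gives no alpha, power, effect size or denominator for them. The only background figure is in Section 18.9b: "most studies find 60% complication rates across the world and 30% readmission rates". That sentence states no time window and no definition.

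No section mentions discharge to a rehabilitation, nursing or other facility. None says how such patients are handled, or that discharge destination is recorded.

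**The concern.** The definition sets two conditions: an admission to any hospital by Day 90, and a discharge home before it. A patient sent from the index stay to a facility and readmitted from there meets the first condition but not the second. As written, that admission is not counted.

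Two things are at stake. First, the count of readmissions is too low by however many are made directly from a facility. Second, the loss need not be equal between arms. Destination is decided after randomisation, and complications, the outcome that SIM is meant to reduce, may influence it. If fewer complications on SIM sent more SIM patients home, more SIM readmissions would qualify and more ONS readmissions would drop out, which would work against a true benefit.

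**Working it through.** **The plan's own figures.** There is none to reproduce for readmission: no rate, power or sample size is attached to it. The sample size in Section 11.1 (146, then 146/0.77 = 189.6, taken as 190, then 190/0.95 = 200) is built on the 30-day complication rate and does not use readmission.

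**Which pathways count.** Taking Section 10.2e literally, with the admission by Day 90:

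| Pathway after the index stay | Discharge home before the admission? | Counted? |
|---|---|---|
| home, then hospital | yes | yes |
| facility, then home, then hospital | yes | yes |
| facility, then hospital | no | no |

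Only the third pathway is lost.

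**Size: inputs.**
- Overall readmission rate: 30% (Section 18.9b), taken here as the rate from any destination.
- f, the share discharged to a facility: not in the documents; assumed 5% to 20%.
- k, the readmission rate in facility patients relative to the others: not in the documents; assumed 1.0 to 1.5.

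**Size: formulas.** Let r be the readmission rate in patients discharged home. Then 0.30 = (1 − f)r + fkr, so r = 0.30/(1 − f + fk). If no facility patient goes home before readmission, the counted rate over all patients is (1 − f)r, and the share of readmissions missed is fk/(1 − f + fk). If half of the facility patients' readmissions follow a return home, the share missed is halved.

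| f | k | r | Counted rate | Share missed, none home first | Share missed, half home first |
|---|---|---|---|---|---|
| 0.05 | 1.0 | 30.0% | 28.5% | 5.0% | 2.5% |
| 0.10 | 1.0 | 30.0% | 27.0% | 10.0% | 5.0% |
| 0.20 | 1.0 | 30.0% | 24.0% | 20.0% | 10.0% |
| 0.05 | 1.5 | 29.3% | 27.8% | 7.3% | 3.7% |
| 0.10 | 1.5 | 28.6% | 25.7% | 14.3% | 7.1% |
| 0.20 | 1.5 | 27.3% | 21.8% | 27.3% | 13.6% |

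For the last row: r = 0.30/(0.80 + 0.30) = 0.30/1.10 = 27.3%; counted = 0.80 × 27.3% = 21.8%; missed = 0.30/1.10 = 27.3%. Per 200 patients, the registered total in Section 11.1, 30% is 60 readmissions, so the missed number runs from 60 × 0.05 = 3 to 60 × 0.273 = 16.4. Fewer than 200 will actually be discharged after surgery, so these are slightly high.

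A different set-up gives much the same range. Hold the rate at 30% in patients discharged home and let it be 30% to 50% in facility patients. The share missed then runs from 5% to 0.20 × 0.50/(0.80 × 0.30 + 0.20 × 0.50) = 0.10/0.34 = 29%.

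**Denominator.** The counted rates above keep facility patients in the denominator. If the denominator were only patients discharged home, the reported rate would be r: 30% when k = 1.0, so no understatement, and 27.3% at worst (f = 0.20, k = 1.5).

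**Between arms.** If f and k are the same in both arms, each counted rate is the true rate times (1 − f)/(1 − f + fk). The ratio between arms is unchanged and the absolute difference shrinks in proportion. If the true rate is 30% in both arms and k = 1.0, but the facility shares are 20% and 10% (assumed), the counted rates are 0.30 × 0.80 = 24% and 0.30 × 0.90 = 27%: a spurious difference of 3 points. With only patients discharged home in the denominator, both would read 30%.

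**The case against.** The strongest reply is that the wording is loose rather than a deliberate exclusion. The protocol elsewhere treats leaving hospital and going home as one event. On leftover drinks, Section 7.4d says: "If the patient is discharged from the hospital before consuming all 5-day supply of study product, the remaining should be sent home". The post-surgical stool sample is tied to hospital discharge in Section 7.4e and to the return home in Section 15.2. On that view, discharge home simply means the end of the index stay, and sites would code it so. This stands as a plausible account of intent. It does not remove the problem: nothing in the documents says so, 10.2e is the only definition, and two sites could code the same patient differently.

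Other parts of the reply stand in full:
- A reader might infer that patients discharged to a facility are never counted. The text does not support that, because facility to home to hospital by Day 90 meets the definition.
- A reader might infer that the reported rate would fall from 30% to about 22%. That is the extreme corner of assumed inputs. It also needs every facility patient's readmission to come before any return home, and facility patients to stay in the denominator, which the plan does not specify.
- A reader might infer that the arm comparison is biased, and in a known direction. The documents give no facility share in either arm. Bias is possible; its size and sign are not established.
- Complications are graded by the surgeon at Days 30 and 90 (Sections 7.7b and 7.8) without any condition on discharge destination. The morbidity behind a readmission from a facility is therefore still assessed. The assessment forms are not in the documents, so what sites actually record about readmission cannot be checked.

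**Conclusion.** The point holds in a limited form. The sole definition of a named secondary endpoint, applied as written, leaves out readmissions made directly from a facility, and no other section corrects it. On assumed inputs, at most about 5% to 27% of readmissions would be missed, and about half that if half of the facility patients' readmissions follow a return home. Apart from the 30% readmission rate, those inputs are not in the documents, so the range illustrates the loss and does not estimate it. A between-arm effect is possible because destination follows randomisation, but it cannot be sized or given a direction from the documents. The primary endpoint and the sample size are unaffected. The definition should be corrected because the change is small and the literal count is wrong for the stated objective.

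**What to change.** In Section 10.2e, replace the discharge-home condition with discharge from the index cystectomy hospitalisation to any destination (home, rehabilitation or nursing facility), keeping the window through Day 90. State the denominator as patients discharged alive from the index stay. It would help to record the discharge destination and to say how a direct transfer between hospitals is treated, so that a transfer is not coded as a readmission.

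The cost is one phrase and a sentence in 10.2e, plus matching form instructions. If sites have already been coding by the literal rule, patients discharged to a facility would need one data query. Sample size, the primary analysis and the visit schedule do not change.
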